The primary aim is to determine the efficacy of training with this exoskeleton and its ability to improve transfers to standing and sitting as assessed by the five times sit-to-stand test. A secondary aim will be to assess effects of the device during overground ambulation. Outcome measurements to investigate changes of knee range of motion and loading of the paretic limb will be accomplished using an instrumented goniometer; changes in limb loading will be monitored using a foot pressure mapping system; and stepping parameters will be recorded using the GaitRite carpet. An exploratory outcome of changes in energy expenditure during ambulation with and without the powered exoskeleton will be assessed from a 6-minute walking test using a portable metabolic cart. Another exploratory outcome measures of QOL will be determined using the SF-36 and

the Stroke Specific Quality of Life Scale. Additional exploratory outcomes to measure body composition, bone mineral density changes will be assessed using Dual X-ray Absorptiometry (DXA). Additional exploratory outcomes include measuring changes in cortical, corticospinal and spinal excitability in response to brain, spinal and peripheral nerve stimulation (PNS), and brain activation using electroencephalogram (EEG).

Baseline testing for both groups will be performed while ambulating without the device and prior to starting in the training program. The exoskeleton group will repeat testing within the first 3 sessions of the training program. Mid-point assessments will be obtained after 12 and 24 sessions of training. Post assessments will be obtained after 36 sessions of training. Retention will be assessed by repeating the assessments without the exoskeleton after 1 month of stopping the training program.

It is anticipated that longitudinal training with the device will increase number of squats achievable, increase knee flexion during swing, increase loading of the paretic limb, and induce symmetrical stepping. No immediate effect on energy expenditure by the device is expected however, a training effect is expected to demonstrate improvement in the energy cost of ambulation. Any gains observed during this study may not be retained, but as this device has the potential to be used in the home and community environment, justifying a prescription of this device for retention purposes may be warranted. Use of this device may also lead to improvement of QOL.

2. Specific Aims

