During ambulation, stroke survivors reduce loading of the paretic lower extremity (LE) by decreasing the amount of weight and time spent loading the limb (1). Alterations in gait combined with general decreased activity are associated with reduced muscle strength of the paretic LE (4). The combination of LE weakness and altered gait can lead to cardiovascular deconditioning and reduced QOL. In effort to increase mobility to a greater extent than that of ambulation with use of typical passive orthotics, powered exoskeletons are being developed to enhance or enable persons with stroke to ambulate thus promoting the use of their paretic limb. These powered devices use motors that power joint rotation to assist the stepping action during ambulation. Learning to ambulate independently in these devices is difficult and lengthy (5, 6). A new powered orthotic exoskeleton, which powers only the knee joint by monitoring volitional movement of the hip joint offers a simple and intuitive approach to assist with ambulation. The range of motion (ROM) of the knee can be adjusted to assist with knee flexion during the swing phase and knee extension during the stance phase of gait. The level of assistance and intuitive activation of this device is hypothesized to promote greater use of the paretic limb in persons with stroke.

The purpose of this pilot project is to investigate the use of a powered orthotic exoskeleton that provides active assistance to the knee joint in persons with impaired gait due to stroke. This pilot project will assess the changes in use of the paretic LE, energy expenditure of walking with and without the powered orthotic exoskeleton, measure longitudinal changes in QOL, bone density, body composition, neuronal excitability, and brain activation. Promoting greater use of the paretic limb in stroke survivors is expected to improve the energy cost of walking and QOL. The results of this work are anticipated to power future investigations of using powered orthotic exoskeletons in the home and community environments to improve ambulatory ability, functional capacity, and thus further improve QOL. The potential for associated benefits for improved cardiovascular function will also be explored in future studies.

Primary Aim: To determine the change in the ability to squat (LE power) as measured by the Five Times Sit to Stand Test (5xSTS), while wearing and not wearing the powered exoskeleton.

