The 5xSTS is used to determine leg power and an aspect of transfer skill. This test will be used to assess a level of improved function while wearing the device. It will also be used to determine if any training effect is observed after 3 months (36 sessions) of training when not wearing the device.

Secondary Aim: To determine the efficacy of ambulation training using a powered orthotic exoskeleton on knee ROM and loading of the paretic LE while ambulating over ground with and without the device for 3 months (36 sessions).

Multiple outcome measures will be used to determine the effect of the powered exoskeleton on a person's gait biomechanics and functional competency. An instrumented goniometer will record knee joint angles during multiple gait cycles to assess changes in knee flexion during the swing phase. Because the powered orthotic exoskeleton provides stability during the stance phase, stepping parameters will be assessed using an instrumented carpet to determine if the paretic limb has more equitable and symmetrical load.

Secondary Aim: To determine the energy expenditure of ambulation with and without the powered orthotic exoskeleton at baseline and 3 months (36 sessions) post training.

A portable metabolic cart will assess oxygen consumption during the two ambulation conditions (i.e., with and without the device) over a 6-minute period. It is anticipated that the baseline comparison test will not show any metabolic changes due to the added weight of the device and negate any metabolic benefit from the motors powering the knee joint movement. However, a training effect over the 3 months (36 sessions) compared to baseline is anticipated due to the participant becoming more comfortable with the device, thus using the paretic LE more effectively.

Exploratory Aim: To determine the retained function (squatting, knee ROM, paretic LE loading and energy expenditure) 1-month post cessation of training without the device.

It is not known whether any benefits from training will be retained, but if benefits exist while wearing the device, but are not retained, then long term use may be indicated.

Exploratory Aim: To determine differences in QOL measurements (SF36 and Stroke Specific Quality of Life Scale [SS-QOL]) over 3 months (36 sessions).

The mobility portions of the SSQOL and SF36 will be used to determine whether changes in ambulation affect QOL in persons post stroke.

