The loading profile obtained from the F-Scan foot pressure system will be normalized over the gait cycle as percentage of gait cycle and percentage of body weight for each foot. The total area under the curve will be calculated to obtain a total load on each lower extremity. Peak measurements from heel strike and toe-off will be calculated from the curve along with mid stance where load is typically diminished. Maximum knee flexion angles from 10 continuous steps will be averaged for each limb.

Metabolic measurements (VO_2 , HR and RR) will be recorded as averages every minute. Energy cost of distance travelled will be calculated by dividing VO_2 normalized to body weight (ml/kg/min) by the distance traveled (ml/kg/m). The 6 values from the consecutive 1-minute recordings will be averaged for sitting and walking conditions.

Descriptive statistics will be employed for demographic and Fugl-Meyer data. A single group, repeated measures design will be employed in the experimental group to test the within-group effect of using the powered exoskeleton. A two group repeated measures design will be employed to test the between-group differences in outcomes. All outcome measurements will be analyzed using a mixed model ANOVA to determine significant main and interaction effects of group (control, experimental) and time (baseline, session 36, 1-month follow-up). A similar mixed model ANOVA will be used to determine significant main and interaction effects of the two conditions (without [w/o] and with [W] Keeogo exoskeleton) in the experimental group for the 3 time points (baseline, session 36, 1-month follow-up). Post hoc analyses of significant data will be performed using t-tests.

Table 3: Timeline of activities to complete the study

TIME LINE	Year 1				Year 2			
	Q1	Q2	Q3	Q4	Q1	Q2	Q3	Q4
Start-up Activities								
IRB & R&D	x				x			x
Staff Hiring and Training	x							
Purchase Equipment	x							
Database development	x							
Participant Screening	x	x	x	x	x	x		
Participant Enrollment	3	4	4	3	1	0		
Database management	x	x	x	x	x	x		
Abstract writing				x	x	x		
Manuscript writing					x	x		

Potential Difficulties and Limitations

The greatest hurdle in conducting investigations with devices is recruiting participants and completing the training as well as obtaining regulatory approval to conduct the study. Feasibility to enroll and complete the 15 participants is

Protocol ASS-20-01

MIRB# 01929

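### The analysis section searches almost all outcomes for significance with no multiplicity control and does not use the ranking in the aims, which is itself inconsistent for energy expenditure

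*Combined protocol and SAP*

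**What the plan says.** In section 2a, under the heading Description of Data and Statistical Analyses, the protocol sets one rule for almost everything measured: "All outcome measurements will be analyzed using a mixed model ANOVA to determine significant main and interaction effects". The factors are study arm and time, with three time points: before training, after session 36 and one month later. A second family of models follows for the exoskeleton group: "A similar mixed model ANOVA will be used to determine significant main and interaction effects of the two conditions". These compare performance with and without the device over the same time points. Then: "Post hoc analyses of significant data will be performed using t-tests". The one stated exception is "Descriptive statistics will be employed for demographic and Fugl-Meyer data". The text available gives no significance level, no adjustment for multiple tests, and no contrast or time point that counts as primary.

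Section 2, Specific Aims, does rank the outcomes. The Primary Aim rests on 5xSTS alone. Knee range of motion and paretic loading come under a Secondary Aim. Retention, quality of life, DXA, neuronal excitability and EEG come under Exploratory Aims.

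Energy expenditure has two ranks. The opening summary says "An exploratory outcome of changes in energy expenditure during ambulation with and without the powered exoskeleton"; the Specific Aims say "Secondary Aim: To determine the energy expenditure of ambulation with and without the powered orthotic exoskeleton at baseline and 3 months". Table 2 also schedules 10mWT, TUG and 6MWT, yet no aim covers the first two or the distance walked in the third.

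**The concern.** A ranking of aims limits false findings only if the analysis uses it. Here an exploratory bone density result and the primary 5xSTS result pass through the same search, at the same unstated threshold, with the same follow-up t-tests. A report that kept to this section could call any of them significant on equal terms.

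The trial randomizes 15 people (10 and 5) and expects 12 to complete. Estimates will be imprecise, and results picked out because they are significant will tend to overstate the effect. The Specific Aims say the results are meant to power later studies, so an inflated estimate could carry forward into a later design.

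**Working it through.** **No figure to reproduce.** The plan states no significance level, power or number of tests. I assume a two-sided 0.05 level.

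**Inputs.** Outcomes come from the Specific Aims, the outcome descriptions, Table 2 and the statistical section. Fugl-Meyer is left out as descriptive. The plan does not say how many variables each instrument contributes, so I counted at three levels of detail.

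(a) *One variable per instrument.*
- Group by time: 5xSTS, carpet, foot pressure, energy expenditure, knee range, 10mWT, TUG, 6MWT, EEG, excitability, DXA, SF-36, SS-QOL = 13.
- Condition by time (the first eight, also measured with the device) = 8.
- Total 21.

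(b) *Variables named in the text, one side only.*
- Group by time: 5xSTS 1, carpet 3, foot pressure 4, metabolic 4, knee 1, walking and mobility tests 3, EEG 1, excitability 3, DXA 5, quality of life 2 = 27.
- Condition by time: 1 + 3 + 4 + 4 + 1 + 3 = 16.
- Total 43.

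(c) *Both limbs or sides, and sitting as well as walking.*
- Group by time: 1 + 5 + 8 + 7 + 2 + 3 + 1 + 3 + 7 + 2 = 39.
- Condition by time: 1 + 5 + 8 + 7 + 2 + 3 = 26.
- Total 65.

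More SF-36 or SS-QOL subscales, EEG measures or recorded muscles would raise these counts. The documents do not give those numbers.

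**Formulas.** With k tests and no true interactions, the expected number of false findings is 0.05 × k, whatever the correlation between tests. The chance of at least one, if the tests are independent, is 1 − 0.95^k.

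| Count | k | Expected false interactions | Chance of at least one (independent) |
|---|---|---|---|
| (a) | 21 | 1.05 | 66% |
| (b) | 43 | 2.15 | 89% |
| (c) | 65 | 3.25 | 96% |

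The between-group models alone give 0.05 × 13 = 0.65 to 0.05 × 39 = 1.95.

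**Correlation.** The outcomes are related: VO2 with energy cost, load area with its peaks, one limb with the other. Both model families also reuse the exoskeleton group's without-device data. Taking 43 tests as equally correlated normal statistics, the chance of at least one false finding is 77%, 59% and 38% at assumed correlations of 0.3, 0.5 and 0.7. The expected number stays at 2.15; the false findings cluster.

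**If inference is limited to 5xSTS.** One interaction test at 0.05 gives 0.05 expected false findings. Two tests at 0.05 each give a familywise error of 1 − 0.95² = 9.8% if independent; at 0.025 each it is 1 − 0.975² = 4.9%. Holm holds it at or below 5% without assuming independence.

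**The case against.** The strongest reply is that this is a small pilot, that the aims already rank the outcomes, and that t-tests run only after a significant ANOVA. Much of that stands, and it rules out several stronger readings.

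- *Nothing ranks the outcomes.* Not so. 5xSTS is the only primary measure, and energy expenditure is the only one given two ranks. The gap is that the analysis section does not use the ranking, and that three scheduled tests have no rank.
- *Every outcome is tested.* Fugl-Meyer is assigned descriptive statistics, although the wording about all outcome measurements pulls the other way.
- *Three false findings should be expected.* Three needs 3 / 0.05 = 60 interaction tests, so nearly the finest count with both model families pooled.
- *Main effects multiply the problem threefold.* They would give 63 to 195 F-tests, but treating significant main effects as false assumes that none is real. Both groups train for 36 sessions, so time effects are expected, and the motor drives the knee, so a device effect on knee angle is expected.
- *A false finding is almost certain.* That needs independent tests, which these are not.
- *Significance will choose the next trial's endpoints.* No text says so. The documents speak of powering later work and, for the 2:1 ratio, of safety and feasibility data.

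Running t-tests only after a significant ANOVA gives partial protection within one outcome and none across outcomes. The pilot label lowers the stakes. It does not fit a plan that words its primary aim as efficacy and looks for significant change even in its exploratory outcomes.

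**Conclusion.** The point holds in a limited form. The plan looks for significant effects in all outcomes other than Fugl-Meyer, in two model families, with no stated error control and without using its own ranking. Energy expenditure has two ranks and three tests have none. 5xSTS itself falls under both models with no primary contrast or time point.

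About 1 to 3 false interaction findings are expected. The chance of at least one is 66% to 96% under independence and lower with correlation. These figures rest on an assumed 0.05 level, no true interactions and my counts of variables. This is a worthwhile low-cost correction, not a flaw that undermines the pilot.

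**What to change.** In section 2a, under the heading Description of Data and Statistical Analyses:

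1. State that only the 5xSTS questions are inferential. Name one contrast and one time point for the between-group question (without the device) and one of each for the with-versus-without-device question in the exoskeleton group. Choose a time point at which Table 2 schedules the measurement; it shows no with-device testing at 1 month.
2. State the significance level. If both questions are primary, use Holm or a fixed testing order.
3. Report all other outcomes as estimates with 95% confidence intervals, labelled exploratory for inference, with no t-tests triggered by significance.
4. Give energy expenditure the same rank in the opening summary and the Specific Aims, and assign a rank to 10mWT, TUG and 6MWT distance.

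This changes wording only and adds no participants, visits or measurements. The cost is that fewer results can be called significant.

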This device separates itself from the other powered exoskeleton devices (e.g., Indego, Ekso) because it only provides assistance to the knee joint and requires the user to have some ability to ambulate independent of the device. Therefore, the user must be able to initiate the active movement, which will then be enhanced by assistance from the Keeogo. The system assists the knee to enhance user-initiated movements by using kinetic and kinematic data from sensors located at the knee and hip joints to assist in all phases of the gait cycle, i.e. knee flexion and extension in swing phase, knee extension (both eccentric control and concentric assist) in stance phase. In addition to gait, the device assists during other functional lower extremity activities, i.e. squatting motions, kneeling, walking, stair climbing and stand-sit/sit-stand transfers. Keeogo™ has two essential functions: (1) to provide kinematic amplification during the swing phase of gait and (2) to provide stability for the stance phase of gait through knee bracing coupled with non-linear spring-like assistance. Keeogo™ is designed to operate intuitively through automatic sensing and augmenting the user's natural walking movement. The eccentric control assists during the gait cycle at initial contact (loading response), squat (Figure 5), kneel, stand to sit and stairs. The eccentric control applies the torque gradually, thus stabilizing the knee and preventing buckling.

Figure 5: Squatting in the Keeogo

Outcome Measurements and Testing sessions: The timeline for conducting testing sessions is outlined in Table 2. Screening participants and obtaining their medical history and demographics will be obtained once, prior to initiating training. Baseline assessments that do not involve the exoskeleton will be obtained prior to training in both groups. Baseline assessments, which involve the exoskeleton (for the exoskeleton group only) will be obtained during the first three sessions after the participant has been correctly fitted and acclimated to the exoskeleton. Testing will be repeated after training session 36 (3 months) without the exoskeleton for both groups and repeated with the exoskeleton for the exoskeleton group. All participants (control and experimental) will be asked to return 1-month post cessation of training for a follow-up visit where all the outcome measures will be repeated without the exoskeleton for both groups (Table 2) to assess retention of functional gains.

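### The with/without-device ANOVA in the exoskeleton group includes a 1-month with-device cell that the design never collects, so part of the stated interaction and any three-time condition effect are not estimable

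*Combined protocol and SAP*

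**What the plan says.** The section Description of Data and Statistical Analyses gives two models. One compares groups over baseline, session 36 and 1-month follow-up. The other is confined to the exoskeleton group and tests main effects and an interaction for these factors: "two conditions (without [w/o] and with [W] Keeogo exoskeleton) in the experimental group for the 3 time points (baseline, session 36, 1-month follow-up").

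Three other places fix the condition of the 1-month assessment:

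- Opening summary, before section 2: "Retention will be assessed by repeating the assessments without the exoskeleton after 1 month of stopping the training program".
- Section 2, Specific Aims, exploratory aim on retention: "To determine the retained function (squatting, knee ROM, paretic LE loading and energy expenditure) 1-month post cessation of training without the device".
- Outcome Measurements and Testing sessions: a "follow-up visit where all the outcome measures will be repeated without the exoskeleton for both groups".

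The same testing-session section says that both conditions are collected at session 36, where testing is "repeated after training session 36 (3 months) without the exoskeleton for both groups and repeated with the exoskeleton for the exoskeleton group". With-device baseline data for the exoskeleton group come from the first three sessions.

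The primary aim is the change in squatting ability "as measured by the Five Times Sit to Stand Test (5xSTS), while wearing and not wearing the powered exoskeleton". The text below it fixes the training part (without the device, after 36 sessions) but gives no time point or comparator for the device part. The energy-expenditure aim is stated at two times only: "To determine the energy expenditure of ambulation with and without the powered orthotic exoskeleton at baseline and 3 months (36 sessions) post training".

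**The concern.** The within-group model crosses two conditions with three times and asks for the full interaction, yet the plan collects with-device data at only two of those times. This is not dropout. The cell is missing for every participant because the design puts the 1-month visit without the device.

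The model matters because it is the only one given for the with/without comparison, which is part of the primary aim. If it goes into the analysis as worded, the output will either be an error or a test that differs from the one described. The effect reported as the condition by time interaction would then not be the effect that the plan defines.

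**Working it through.** The plan gives no figure to reproduce here (no power, alpha, SD or effect size), so the check is structural.

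**Inputs.** Conditions and times come from Description of Data and Statistical Analyses. The condition at each time comes from Outcome Measurements and Testing sessions, confirmed by the opening summary and section 2. The group size of 10 comes from the Randomization paragraph.

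**Cells.** Write a for without device and b for with device.

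| | Baseline | Session 36 | 1 month |
|---|---|---|---|
| Without | a0 | a36 | a1 |
| With | b0 | b36 | b1: not collected |

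The model needs 2 × 3 = 6 cells; the design supplies 5.

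**Rank.** With W = 1 for with-device and indicators T36 and T1 for the later times, the mean is

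β0 + β1·W + β2·T36 + β3·T1 + β4·W·T36 + β5·W·T1.

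The product W·T1 is non-zero only in cell b1. In the five collected cells that column is all zeros, so the rank is 5 of 6, against 6 of 6 if b1 existed.

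**What is lost.** Any contrast that needs b1:

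- (b1 − a1) − (b0 − a0) = β5, which is one of the two interaction df;
- the condition effect averaged over three times, (b0 + b36 + b1)/3 − (a0 + a36 + a1)/3;
- the condition-averaged change from baseline to 1 month, (a1 + b1)/2 − (a0 + b0)/2.

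**What remains.**

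- device effect at baseline, b0 − a0; at session 36, b36 − a36; and the average of the two;
- change in the device effect from baseline to session 36, (b36 − a36) − (b0 − a0) = β4;
- without-device changes a36 − a0, a1 − a0 and a1 − a36.

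**Fit check.** Data were simulated for 10 people with the five collected cells. A standard repeated-measures ANOVA routine (statsmodels AnovaRM) stopped because the data were unbalanced. A mixed-model routine (statsmodels MixedLM) with the full condition by time terms stopped on a singular matrix. Least squares with person effects and a generalised inverse did run, and gave a 1-df interaction test on 50 − 10 − 4 = 36 residual df.

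**Restricted model.** Condition by time with baseline and session 36 only has four cells and rank 4 of 4. In the simulation it ran without error, with each effect on 1 and 9 df at n = 10. A mixed model on the five cell means also fitted.

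**Group by time model.** On without-device data, both groups are tested at all three times. All six of its cells are collected.

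**The case against.** The strongest reply is that this is a wording slip with little effect in a 15-person pilot. Much of that stands.

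First, a reader might infer that the analysis cannot be run at all. That goes too far. Some software drops or generalises over the aliased column and gives output. An additive model (condition plus time) is full rank at 4 of 4, and its condition effect puts weights −0.5, −0.5, 0, 0.5, 0.5 on a0, a36, a1, b0, b36. That is the device effect averaged over baseline and session 36. The plan does not define its condition effect as a three-time average, so this estimable version is open to it. What does not survive is the interaction as stated, because one of its two df has no data behind it.

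Second, since the plan says "Post hoc analyses of significant data will be performed using t-tests", a reader might infer that device contrasts can be reached only after an ANOVA that fails, or that the analyst will have to choose a model with the results in view. The documents do not support either reading. Condition has two levels, so its effect is itself the with/without comparison. The empty cell is known from the design and can be dealt with before any data exist.

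Third, a reader might argue that the choice among device contrasts changes precision two-fold. With equal correlations the standard errors of the two-time average, the session-36 effect and the interaction stand at 1 : 1.41 : 2. With illustrative correlations of 0.9 within condition over time and 0.6 elsewhere, the variances are 0.7, 0.8 and 0.4, and the ratio becomes 1 : 1.07 : 0.76. The documents give no correlations, so no precision claim can be made.

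Fourth, the with-device baseline is taken slightly later than the without-device baseline. A reader might infer a practice bias in the baseline device contrast, but the documents give no size for it and it may be zero. It does not carry this point.

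**Conclusion.** The point holds in a limited form. The within-exoskeleton model as written includes a cell that the design does not collect: 5 of 6 cells exist, the rank is 5 of 6, and the estimable interaction has 1 df where a full 2 × 3 interaction has 2. Any condition effect averaged over all three times is also not estimable.

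The consequence is modest. Every contrast that the aims need can still be estimated from the planned data, and the group by time comparison is untouched. It is still worth correcting, because this is the only model offered for the with/without part of the primary aim and the test it describes cannot be produced.

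The unnamed effect for the device part of the primary aim is a smaller, separate gap in detail: the plan lists a condition effect and an interaction but does not say which one answers the question.

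The conclusion rests only on the three statements that the 1-month assessment is done without the device. It needs no assumption about variances, correlations or dropout, and it does not depend on the column alignment of Table 2.

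**What to change.** In Description of Data and Statistical Analyses:

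1. Restate the exoskeleton-group model as condition (without, with Keeogo) by time (baseline, session 36).
2. State that 1-month retention is analysed from without-device data only.
3. State whether the condition effect or the condition by time interaction from that 2 × 2 model answers the device part of the primary 5xSTS aim. The training part is already fixed in section 2 and needs no change.

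The cost is two or three sentences. No visit, test or participant is added, and the group by time model stays as it is.
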